12. APPENDICES

12.1. Appendix 1 – Abbreviations and Trademarks

Abbreviations

ACQ	Asthma Control Questionnaire
ACT	Asthma Control Test
ADR	Adverse Drug Reaction
AE	Adverse Event
AESI	Adverse Event of Special Interest
ALT	Alanine Transaminase
AM	Morning
AQLQ	Asthma Quality of Life Questionnaire
AST	Aspartate Transaminase
ATS	American Thoracic Society
AUC	Area Under the Curve
BID	Twice daily
BMI	Body Mass Index
BPM	Beats Per Minute
BST	Bioanalytical Science and Toxicokinetics
BTS/SIGN	British Thoracic Society / Scottish Intercollegiate Guidelines Network
BUN	Blood Urea Nitrogen
CI	Confidence Interval
CONSORT	Consolidated Standards of Reporting Trials
COPD	Chronic Obstructive Pulmonary Disease
DNA	Deoxyribonucleic acid
DMPK	Drug Metabolism and Pharmacokinetics
DPI	Dry Powder Inhaler
ECG	Electrocardiogram
(e)CRF	(Electronic) Case Report Form
eDiary	Electronic Diary
EMA	European Medicines Agency
EOS	End of study
E-RS	Evaluating Respiratory Symptoms
ERS	European Respiratory Society
EU	European Union
EW	Early Withdrawal
FDA	Food and Drug Administration
FeNO	Fractional Exhaled Nitric Oxide
FEV1	Forced expiratory volume in 1 second
FF	Fluticasone Furoate
FP	Fluticasone Propionate
FRP	Female of Reproductive Potential
FSC	Fluticasone Salmeterol Combination

FSH	Follicle Stimulating Hormone
FVC	Forced Vital Capacity
GCP	Good clinical practice
GCSP	Global Clinical Safety and Pharmacovigilance
GINA	Global Initiative for Asthma
GLP	Good Laboratory Practice
GOLD	Global Initiative for Chronic Obstructive Lung Disease
GSK	GlaxoSmithKline
hCG	Human Chorionic Gonadotropin
HIV	Human Immunodeficiency Virus
HPA	Hypothalamic Pituitary Axis
HR-QoL	Health-Related Quality of Life
HRT	Hormone Replacement Therapy
IB	Investigator's Brochure
ICF	Informed Consent Form
ICH	International Conference on Harmonization
ICS	Inhaled Corticosteroids
IEC	Independent Ethics Committee
Ig	Immunoglobulin
IL	Interleukin
IOP	Intraocular Pressure
IP	Investigational Product
IRB	Institutional Review Board
IRT	Interactive Response Technology
ITT	Intent to Treat
kg	Kilogram
L/min	Liters per minute
LABA	Long-Acting Beta-2-Agonists
LAMA	Long-Acting Muscarinic Antagonist
LOCS III	Lens Opacities Classification System III
LRTI	Lower Respiratory Tract Infection
LTRA	Leukotriene Receptor Antagonist
MACE	Major Adverse Cardiac Event
MAOI	Monoamine Oxidase Inhibitors
MedDRA	Medicinal Dictionary for Regulatory Activities
mcg (μ g)	Microgram
MDI	Metered Dose Inhaler
mg	Milligram
min	Minute
mL	Milliliter
MMRM	Mixed-Model Repeated Measures
MSDS	Material Safety Data Sheet
msec	Millisecond
NIH	National Institutes of Health
NYHA	New York Heart Association
OCS	Oral Corticosteroids

PEF	Peak Expiratory Flow
PK	Pharmacokinetic
PM	Afternoon
prn	As needed
QD	Once daily
QTc	QT interval corrected for heart rate
QTcB	QT interval corrected for heart rate by Bazett's formula
QTcF	QT interval corrected for heart rate by Fridericia's formula
RAP	Reporting and Analysis Plan
RBC	Red Blood Cell
RNA	Ribonucleic acid
SABA	Short-Acting Beta-2-Agonists
SAE	Serious Adverse Event
SGRQ	St. George's Respiratory Questionnaire
SPC	Summary of Product Characteristics
SRM	Study Reference Manual
TQT	Thorough QT
ULN	Upper Limit of Normal
UMEC	Umeclidinium
US	United States
VI	Vilanterol
VT	Ventricular Tachycardia
WBC	White Blood Cell
WPAI-SHP	Work Productivity and Activity Impairment-Specific Health Problem

Trademark Information

Trademarks of the GlaxoSmithKline group of companies
DISKUS
ELLIPTA

Trademarks not owned by the GlaxoSmithKline group of companies
NONMEM

12.2. Appendix 2 Liver Safety Required Actions and Follow up Assessments

Liver chemistry stopping and follow up criteria have been designed to assure subject safety and evaluate liver event etiology (in alignment with the FDA premarketing clinical liver safety guidance [[Food and Drug Administration 2009](#)]).

Liver chemistry stopping criteria 1-5 are defined below:

1. ALT \geq 3xULN and bilirubin \geq 2xULN (>35% direct bilirubin) (or ALT \geq 3xULN and INR>1.5, if INR measured)

NOTE: If serum bilirubin fractionation is not immediately available, withdraw study drug if ALT \geq 3xULN and bilirubin \geq 2xULN. Serum bilirubin fractionation should be performed if testing is available. If testing is unavailable, **record presence of detectable urinary bilirubin on dipstick**, indicating direct bilirubin elevations and suggesting liver injury.

2. ALT \geq 8xULN.
3. ALT \geq 5xULN but <8 xULN persists for \geq 2 weeks
4. ALT \geq 3xULN if associated with symptoms (new or worsening) believed to be related to hepatitis (such as fatigue, nausea, vomiting, right upper quadrant pain or tenderness, or jaundice) or believed to be related to hypersensitivity (such as fever, rash or eosinophilia).
5. ALT \geq 5xULN but <8 xULN and cannot be monitored weekly for \geq 2 weeks

When any of the liver chemistry stopping criteria 1-5 is met, do the following:

- **Immediately** withdraw investigational product
- Report the event to GSK **within 24 hours** of learning its occurrence
- Complete the liver event CRF and SAE data collection tool if the event also meets the criteria for an SAE. All events of ALT \geq 3xULN **and** bilirubin \geq 2xULN (>35% direct) (or ALT \geq 3xULN **and** INR>1.5, if INR measured); INR measurement is not required and the threshold value stated will not apply to patients receiving anticoagulants), termed 'Hy's Law', **must be reported as an SAE (excluding studies of hepatic impairment or cirrhosis)**.

NOTE: if serum bilirubin fractionation is not immediately available, withdraw study drug if ALT \geq 3xULN **and** bilirubin \geq 2xULN. Serum bilirubin fractionation should be performed if testing is available. If testing is unavailable, **record presence of detectable urinary bilirubin on dipstick**, indicating direct bilirubin elevations and suggesting liver injury.

- Complete the liver imaging and/or liver biopsy CRFs if these tests are performed
- Perform liver event follow up assessments, and monitor the subject until liver chemistries resolve, stabilize, or return to baseline values as described below.

- Withdraw the subject from the **study** (unless further safety follow up is required) after completion of the liver chemistry monitoring as described below.
- Do not re-challenge with investigational product.

In addition, for criterion 1:

- Make every reasonable attempt to have subjects return to clinic within **24 hours** for repeat liver chemistries, liver event follow up assessments (see below), and close monitoring
- A specialist or hepatology consultation is recommended
- Monitor subjects twice weekly until liver chemistries (ALT, AST, alkaline phosphatase, bilirubin) resolve, stabilize or return to within baseline values

For criteria 2, 3, 4 and 5:

- Make every reasonable attempt to have subjects return to clinic **within 24-72 hrs** for repeat liver chemistries and liver event follow up assessments (see below)
- Monitor subjects weekly until liver chemistries (ALT, AST, alkaline phosphatase, bilirubin) resolve, stabilize or return to within baseline values; criterion 5 subjects should be monitored as frequently as possible.

Subjects with ALT $\geq 5xULN$ and $< 8xULN$ which exhibit a decrease to ALT $x \geq 3xULN$, but $< 5xULN$ and bilirubin $< 2xULN$ without hepatitis symptoms or rash, and who can be monitored weekly for 4 weeks:

- Notify the GSK medical monitor within 24 hours of learning of the abnormality to discuss subject safety
- Can continue investigational product
- Must return weekly for repeat liver chemistries (ALT, AST, alkaline phosphatase, bilirubin) until they resolve, stabilize or return to within baseline
- If at any time these subjects meet the liver chemistry stopping criteria, proceed as described above
- If, after 4 weeks of monitoring, ALT $< 3xULN$ and bilirubin $< 2xULN$, monitor subjects twice monthly until liver chemistries normalize or return to within baseline values.

For criteria 1-5, make every attempt to carry out the **liver event follow up assessments** described below:

[figure not shown]
- Viral hepatitis serology including:
 - Hepatitis A IgM antibody;
 - Hepatitis B surface antigen and Hepatitis B Core Antibody (IgM);
 - Hepatitis C RNA;
 - Cytomegalovirus IgM antibody;

- Epstein-Barr viral capsid antigen IgM antibody (or if unavailable, obtain heterophile antibody or monospot testing);
- Hepatitis E IgM antibody
- Blood sample for PK analysis, obtained within 72 hours of last dose. Record the date/time of the PK blood sample draw and the date/time of the last dose of investigational product prior to blood sample draw on the CRF. If the date or time of the last dose is unclear, provide the subject's best approximation. If the date/time of the last dose cannot be approximated OR a PK sample cannot be collected in the time period indicated above, do not obtain a PK sample. Instructions for sample handling and shipping are in the SRM.
- Serum creatine phosphokinase (CPK) and lactate dehydrogenase (LDH).
- Fractionate bilirubin, if total bilirubin $\geq 2xULN$
- Obtain complete blood count with differential to assess eosinophilia
- Record the appearance or worsening of clinical symptoms of hepatitis or hypersensitivity, such as fatigue, nausea, vomiting, right upper quadrant pain or tenderness, fever rash or eosinophilia as relevant on the AE report form
- Record use of concomitant medications, acetaminophen, herbal remedies, other over the counter medications, or putative hepatotoxins, on the concomitant medications report form.
- Record alcohol use on the liver event alcohol intake case report form

The following are required for subjects with ALT $\geq 3xULN$ and bilirubin $\geq 2xULN$ (>35% direct) but are optional for other abnormal liver chemistries:

- Anti-nuclear antibody, anti-smooth muscle antibody, and Type 1 anti-liver kidney microsomal antibodies.
- Serum acetaminophen adduct assay (quantifies potential acetaminophen contribution to liver injury, detectable by HPLC assay more than 1 week following acetaminophen use) [James 2009].
- Only in those with underlying chronic hepatitis B at study entry (identified by positive hepatitis B surface antigen): quantitative hepatitis B DNA and hepatitis delta antibody.
- Liver imaging (ultrasound, magnetic resonance, or computerized tomography) to evaluate liver disease.

Figure 1 Phase III-IV Liver Safety Algorithms

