4. STUDY DESIGN

4.1. Overall Design

This study employs a multi-centre, active-controlled, double-blind, parallel-group design. At the conclusion of the 3-week run-in period (Visit 2), all subjects who meet the pre-defined criteria will be enrolled to receive FF/VI (100/25 mcg via the ELLIPTA dry powder inhaler [DPI]) once a day, in the morning, during the 2-week stabilization period. At the conclusion of the stabilization period (Visit 3), all subjects who meet the pre-defined criteria will be randomised 1:1:1:1:1 to receive either FF/UMEC/VI (100/31.25/25; 100/62.5/25; 200/31.25/25; 200/62.5/25 mcg) or FF/VI (100/25; 200/25 mcg) via the ELLIPTA DPI once daily in the morning for the duration of the treatment period (see Section 4.2 for further details on study treatment assignment and duration).

Subjects who permanently discontinue study treatment are not required to withdraw from the study. Subjects who have permanently discontinued study treatment and have not withdrawn consent are encouraged to continue in the study and complete all remaining protocol specified clinic visits (see Section 5.6).

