5.6. Withdrawal/Stopping Criteria

5.6.1. Withdrawal from Study Treatment

Subjects who withdraw from double-blind study treatment prematurely (for any reason) should, where possible, continue to be followed-up as per protocol until the completion of the Safety Follow-up assessments (Section 7.1; refer to the SRM for further details). If this is not possible, the Investigator must encourage the subject to participate in as much of the study as they are willing (or able) to.

A subject may be withdrawn from study treatment at any time. A reason for premature discontinuation of study treatment (e.g., AE, lack of efficacy [including acute moderate or severe asthma exacerbation], protocol deviation, Investigator discretion, consent withdrawn etc.) must be captured in the eCRF.

A subject must be withdrawn from study treatment if any of the following stopping criteria are met:

- Liver Chemistry: Meets any of the protocol-defined liver chemistry stopping criteria (see Section 5.6.3 and Appendix 2)
- QTc: Meets any of the protocol-defined stopping criteria (see Section 5.6.4)
- Pregnancy: Positive pregnancy test (see Section 7.5.3 and Appendix 5)

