#### 7.1.4. Strategy for Intercurrent (Post-Randomization) Events

A “treatment policy” strategy will be used to handle all intercurrent events, including treatment discontinuation, use of rescue medication provided for the study or for asthma exacerbations, temporary treatment interruption, or treatment switches.

Participants who discontinue study treatment prematurely are encouraged to stay in the study and return for all clinic visits as planned. Data collected on- or post-treatment discontinuation will be included in the primary analysis, regardless of the use of rescue medications or treatment switches. This analysis corresponds to the “de facto” analysis pre-specified in the protocol and thus referenced throughout this document.

For the primary analysis, no imputation of missing data are planned. Missing data are assumed Missing at Random (MAR) handled via Mixed Model Repeated Measures (MMRM) analysis. To examine the sensitivity of the results of the primary analysis to departures from this assumption, further sensitivity analyses will be performed using alternative assumptions on the missing data.

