The 'de facto' type estimand analysis for the key secondary endpoint includes all moderate/severe asthma exacerbations following discontinuation of randomized treatment for participants who remain in the study and assumes that any remaining missing data due to early withdrawal from study prior to the planned end of study visit is Missing at Random (MAR). To examine the sensitivity of the analysis result to departures from this assumption, further sensitivity analyses will be performed using alternative assumptions analogous to those used for the primary endpoint. For each proposed imputation method, the sensitivity analysis will include both observed (on and post-treatment) and imputed asthma exacerbation events. The following different algorithms are proposed to impute the post-treatment missing data.

These analyses will be performed for weeks 1-52 only.

For each approach, exacerbations in the unobserved period will be imputed only up to the participant's planned end of study visit date determined by participant's randomization date (see Section 11.3.2).

- Tipping Point:

This method will explore the potential effect of missing data on the reliability of the results by using different assumptions regarding the moderate/severe asthma exacerbation rate in participants who withdraw from study early. Participants who withdrew from the study earlier than their planned end of study will have missing data imputed for the period of time between withdrawal from the study to the planned end of study visit first assuming missing at random (MAR) and then multiplying the estimated exacerbation rate under MAR by different deltas. The imputed exacerbation rates will vary independently for FF/UMEC/VI arms and FF/VI arms.

The deltas to be investigated are pre-selected multiples of the observed rate reduction. If the observed rate reduction from the key secondary analysis is  $x$ , the deltas to be investigated will range from  $1-x$  to  $1+3x$  for both active and placebo arms, in increments of  $0.5x$  (For example, if the observed rate reduction is 20% ( $x=0.2$ ) the imputed rates will be multiplied by deltas of 0.8 to 1.6 in increments of 0.1). The increment or range may be refined based on the analysis results and the location of tipping point.

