## 11.7. Appendix 7: Reporting Standards for Missing Data

### 11.7.1. Premature Withdrawals

Element	Reporting Detail
General	
 
• Withdrawal from Study Prior to Randomization               
 
• Participants who are pre-screening failures, screening failures, run-in failures, or stabilization failures (see Protocol Section 5.5 for the definitions) will be reported to account for the participant disposition.
 
 
 
• Withdrawal from Study Treatment               
 
• Randomized participants who withdraw from double-blind study treatment prematurely (for any reason) should, where possible, continue to be followed-up as per protocol until the end of the study, after returning to the appropriate asthma therapy per investigator's discretion. Post-treatment data will be included in the statistical analyses.
 
 
 
• Withdrawal from Study               
 
• See Appendix 2 for details on data collected at the Early Withdrawal visit.
 
 
 
• Participant study completion (i.e. as specified in the protocol) was defined as 'A participant will be considered to have completed the study upon completion of all assessments and procedures for Visit 8/EOS and including a successful follow-up contact/visit.'
 

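### Appendix 2 tells sites to withdraw liver-event subjects from the study, while Section 5.6.1 and SAP 11.7.1 keep them in follow-up

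*Protocol*

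**What the plan says.** Protocol Appendix 2 (Section 12.2) lists what a site must do when any of liver criteria 1 to 5 is met. The first action is to stop investigational product at once. A later, separate bullet tells the site to withdraw the subject from the study, with the word for study emphasized, "unless further safety follow up is required) after completion of the liver chemistry monitoring as described below".

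The body of the protocol takes the other line:

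- Section 4.1: "Subjects who permanently discontinue study treatment are not required to withdraw from the study".
- Section 5.6.1, general rule: "Subjects who withdraw from double-blind study treatment prematurely (for any reason) should, where possible, continue to be followed-up as per protocol". If full follow-up is not possible, "the Investigator must encourage the subject to participate in as much of the study as they are willing (or able) to".
- Section 5.6.1, mandatory stops: "A subject must be withdrawn from study treatment if any of the following stopping criteria are met". The liver criteria are on that list, with a cross-reference to Appendix 2 and no exception to the follow-up rule.

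SAP 11.7.1 restates the rule: "Randomized participants who withdraw from double-blind study treatment prematurely (for any reason) should, where possible, continue to be followed-up as per protocol". The analyses depend on it. SAP 7.1.4 says of the primary endpoint: "Data collected on- or post-treatment discontinuation will be included in the primary analysis". SAP 7.2.5 says the key secondary analysis "assumes that any remaining missing data due to early withdrawal from study prior to the planned end of study visit is Missing at Random".

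**The concern.** For a subject who has stopped drug for a liver event, has completed liver monitoring and is willing to continue, Section 5.6.1 says keep the visits and Appendix 2 says end participation.

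Both the primary and the key secondary analysis use a treatment-policy strategy, so FEV1 and exacerbations after the drug is stopped are meant to be observed. A site that follows Appendix 2 makes them missing by instruction. The primary model in SAP 7.1.6 has no term for being off treatment, so the missing values are in effect predicted from the rest of the arm, most of whom would be expected to be still on drug. That is the gap that post-discontinuation follow-up is meant to close.

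**Working it through.** **Comparing the texts**

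| Question | Appendix 2 | Section 5.6.1 and SAP 11.7.1 |
|---|---|---|
| Stop drug? | Yes, immediately | Yes |
| Leave the study? | Yes, once liver monitoring is complete | No; continue where possible |
| Qualification | Only if further safety follow-up is needed | Feasibility and willingness |
| Exception for liver events? | Not described as one | None stated |

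The qualification in Appendix 2 protects safety follow-up only. It does not restore spirometry, exacerbation or questionnaire visits once the liver tests have settled.

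**The plan's own sample size (Protocol 9.2.1)**

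This is the one stated figure that rests on early withdrawal. Inputs: difference 100 mL, SD 400 mL, two-sided 0.05, 90% power. The two-sample formula gives n = 337 per arm, with power 0.9006 by the normal approximation and 0.8998 by the noncentral t. With 10% missing, 337/0.9 rounds up to 375 randomized. The figure reproduces and is not in dispute.

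**Number of subjects affected**

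- Randomized (SAP 5.4): 766 + 643 + 399 + 631 = 2439, or 406.5 per arm.
- Liver-event rate: not given. Assumed range 0.2% to 1%: 0.002 × 2439 ≈ 5 and 0.01 × 2439 ≈ 24, or about 0.8 to 4 per arm.
- Planned allowance for missing Week 24 spirometry: 375 − 337 = 38 per arm. Four per arm falls within it.
- Even if they were additional to the allowance, power by the normal approximation would be 0.8972 with 4 fewer per arm and 0.8937 with 8 fewer.

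**Exacerbation follow-up lost**

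The Time and Events Table first schedules post-randomization chemistry at Week 12. For a subject withdrawn just after that visit:

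- Planned end Week 24: 24 − 12 = 12 weeks, and 2 × 12/52 = 0.46 expected events at the assumed control rate of 2 per year.
- Planned end Week 52: 52 − 12 = 40 weeks, and 2 × 40/52 = 1.54 expected events.

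Share of all planned follow-up, using the same planned duration in numerator and denominator:

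| Affected | All planned to Week 24 | All planned to Week 52 |
|---|---|---|
| 5 | 5×12/(2439×24) = 0.10% | 5×40/(2439×52) = 0.16% |
| 24 | 24×12/(2439×24) = 0.49% | 24×40/(2439×52) = 0.76% |

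If events are spread evenly over planned durations, any mix of Week 24, 36 and 52 lies between the two columns.

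**Week 24 FEV1**

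SAP 11.3.1 maps an Early Withdrawal visit on Days 57 to 126 to Week 12, and one on Days 127 to 210 to Week 24. Early withdrawal therefore leaves Week 24 missing. If monitoring takes at least 127 − 85 = 42 days after Week 12, the Early Withdrawal visit supplies a Week 24 value. The follow-up lost is then 6 to 34 weeks: for 24 subjects, 24×6/(2439×24) = 0.25% to 24×34/(2439×52) = 0.64%.

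**Cases with no loss**

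An event found at the final visit has no treatment-period follow-up left to lose. An event found at the Week 24 visit already has its primary endpoint value.

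**The case against.** The best defence is that a specific safety appendix overrides a general rule. Section 4.1 is only permissive, Section 5.6.1 says where possible and points to Appendix 2 for liver events, and the emphasis in the bullet suggests intent. The SAP is not an instruction to sites. The Study Reference Manual and the liver algorithm (Figure 1) were not available and may settle practice.

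Part of this stands. Section 4.1 alone creates no conflict, and whether any site withdrew anyone is unknown. But where possible concerns feasibility; it does not naturally cover an order to remove a willing subject. Section 5.6.1 cites Appendix 2 and still makes no liver exception. If sites do treat the appendix as controlling, the data loss follows. Protocol Amendment 01 also removed mandatory withdrawal after unblinding, which points to a general intent to retain subjects.

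A second objection is to the size and the bias. The event rate is assumed, and entry criteria exclude raised ALT and unstable liver disease. Withdrawal just after Week 12 is early, because monitoring must finish first. Leaving because of a measured liver threshold does not by itself make data missing not at random. These points are fair. They keep the grade low, but they do not remove the contradiction.

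**Conclusion.** The concern holds, as a minor point. The Appendix 2 bullet is current text and gives the opposite instruction to Section 5.6.1 and SAP 11.7.1 for a willing subject whose liver monitoring is complete.

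Its size rests on an assumed event rate of 0.2% to 1%: roughly 1 to 4 subjects per arm and at most about 0.8% of planned follow-up in the early-withdrawal case, less if monitoring is long or events surface late. An event found before Week 12 by an unscheduled test could not push the share above the assumed event rate, given even spread over planned durations. Stated power and type I error are not affected. The tipping-point and jump-to-reference analyses in SAP 7.1.5 and 7.2.5 already take in these withdrawals. Confidence is high on the wording; how many subjects were actually withdrawn under it cannot be told from the documents.

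**What to change.** Replace the Appendix 2 bullet with text to this effect:

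> *Permanently discontinue investigational product. During and after liver chemistry monitoring, the subject should, where possible, keep the scheduled study visits under Section 5.6.1, or as many as they are willing or able to attend, together with any further safety follow-up needed, unless consent is withdrawn.*

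The immediate drug stop, the monitoring schedule and the ban on rechallenge stay as they are. Check that Figure 1 and the Study Reference Manual agree. No SAP change is needed.

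The cost is one bullet, by amendment or site letter, and it helps only subjects still in the study. The SAP already reports 2439 randomized, and SAP 11.3.2 fixes planned final visits by randomization date, so that number may be small or zero. If visits are complete, match the liver-event listings (61 to 64) to the listing of reasons for study withdrawal (Listing 3) and report the number affected per arm. No new data are required.
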